PREVIOUS WORK

Based on emerging work, and preliminary data from our research group,³¹ the implementation of blood flow restriction training (BFRT) may be an advantageous tool to implement in the early post-operative period to combat quadriceps muscle weakness.³² BFRT has been shown to be an effective alternative to high load resistance training (HL-RT) with comparable muscular and physiological benefits.^{33,34} Previous work in young adults demonstrated that the use of BFRT mitigates quadriceps atrophy after ACLR.²⁷ Similarly, in adult patients, the use of BFRT in the early post-operative stages after ACLR has shown comparable improvements in quadriceps strength to HL-RT, and greater improvements in functional strength measures and self-reported function.²⁹ Together, these results are promising. However, there is limited knowledge pertaining to the impact of BFRT on quadriceps strength and function after ACLR in an adolescent age group.

The overall objective of this study is to investigate the impact of BFRT on isometric and isokinetic knee extension strength, quadriceps hypertrophy, and patient reported outcomes after ACLR at 5 different time points in the rehabilitation process. Adolescents and young adult patients undergoing ACLR at our institution and will be recruited to use BFRT for 8 weeks as part of their treatment compared to a standard ACL rehabilitation group at our institution

RESEARCH QUESTION

The purpose of this study is to compare the addition of a BFRT based exercise protocol to a standard ACL rehabilitation protocol in adolescents. Does the addition of BFRT-based exercise improve strength, hypertrophy, and patient reported outcomes after ACL reconstruction in the adolescent population?

PURPOSE OF THE RESEARCH, AIMS AND HYPOTHESES

The specific aims of this study are as follows.

Primary Aim 1: Determine if adjunct BFRT during ACLR post-surgical rehabilitation impacts isometric and isokinetic strength lower extremity strength, when compared to a control group receiving the standard of care rehabilitation.

Hypothesis 1a: We hypothesize that isometric knee extension peak torque and limb symmetry will be greater in the BFRT group compared to the control group at 8 and 12 weeks after ACLR.

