Hypothesis 1b: We hypothesize that isokinetic knee extension peak torque and limb symmetry will be greater in the BFRT group compared to the control group at 6 months and time of return to sport after ACLR. Hypothesis 1c: We hypothesize that the BFRT group will show a greater change in strength from pre-operative testing to 8 weeks post-operative from the control group.

Primary Aim 2: Determine if BFRT during ACLR post-surgical rehabilitation improves patient-reported outcomes (IKDC, KOOS, ACL-RSI) compared to the control group. We hypothesize that the BFRT group will show greater self-reported function and confidence as compared to the control group at all study time points.

Secondary Aim 1: Determine if the use of BFRT during ACLR post-surgical rehabilitation increases mid-thigh

circumference when compared to a control group. We hypothesize that the BFRT group will demonstrate five percent or greater difference in mid-thigh circumference than the control at all study time points.

OUTCOMES DEFINITIONS / DATA POINTS COLLECTED

1) Demographic information:

_		
	a. Age	h. Surgeon
	b. Medical record number	i. Sport
	c. Date of ACL surgery and related surgeries	j. Level of competition in sport
	d. Date of Injury	k. Weight, Height and BMI
	e. Sex	I. Race
	f. Graft Type	m. Insurance status (Public/Private)
	g. Concomitant pathology/Meniscal tear type, laterality	n. Weight bearing status (number of weeks)
	h. Surgeon	

Primary Outcomes Definitions

Active knee range of motion: Knee AROM will be measured in supine position using a goniometer and standardized procedures reported by Norkin and White.³⁵

Mid-thigh circumference will be used to measure and track muscle hypertrophy.

10 Repetition Max Test: The 10 repetition max test will be used to determine an estimate 1 rep maximum on the Shuttle Leg Press machine, as this is a safe and reliable alternative to predicting a 1 rep maximum.

Isometric thigh strength: Preoperative, 8 week and 12 weeks, 6 months and return to play assessments will measure maximum isometric muscle torque using an isokinetic dynamometer (Humac CSMi USA, Stoughton, MA, USA). Return to play assessments will occur at approximately 9 months post-operative.

Isokinetic thigh strength: For assessments at 6 months and time of return to play, maximum muscle torque will be assessed using an isokinetic dynamometer (Humac CSMi USA, Stoughton, MA, USA).

Patient Reported Outcomes:

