Once identified as a potential candidate, the study purpose and protocol will be explained and a brief summary of the study will be provided at the conclusion of the pre-operative appointment. Patients must meet all the requirements of inclusion and exclusion criteria to be eligible for consent.

Consent: Consenting will take place at the pre-operative visit. The patient/parent will be given a detailed description of the purpose and methodology for this study. They will have the opportunity to read the consent forms and ask any questions they may have about the research. If they agree to participate, they will be asked to sign the consent form and a copy will be provided to the patient and family. All consenting documents will be stored in REDCap

If patients agree to enroll, all demographics and information listed in the protocol will be stored in REDCap on a data collection sheet that is listed in the attachments. This sheet will be used to record all pertinent information for all active participants on the study and will be stored in REDCap

Retention: Eligible patients will be required to be seen for a minimum of 80% of patient visits to be included in this study.

Data Collection:

Prior to completing enrollment measures, patients will provide written informed consent to participate in the study. Data collection will occur at five different time points during the rehabilitation process: preoperatively, 8 weeks, 12 weeks, 6 months, and time of return to play. Return to play assessments will be completed at approximately 9 months post-operatively. The schedule of study assessments is listed in Table 1 below.

Table 1. Schedule of Study Procedures and Assessments						
Procedure	Pre-operative	8	12	6	Return	2 year
	Screen	weeks	weeks	months	to Play	follow-up
Informed Consent	x					
Background Information	x					
Patient Reported Outcomes	x	Х	х	х	х	x
Estimated 1 rep Max	X					
Mid-thigh circumference	X	х	Х	х	х	
Isometric thigh strength	X	Х	х	х	Х	
Isokinetic thigh strength				х	х	
Range of motion (ROM)	X	X***	х	х	х	
***ROM will be assessed and collected at each treatment visit for the first 8 weeks after surgery						

Primary Outcomes (See table below):

Active knee range of motion: Knee AROM will be measured in supine position using a goniometer and standardized procedures reported by Norkin and White.³⁵

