Mid-thigh circumference will be used to measure and track muscle hypertrophy. Circumferential measurements has been shown to be valid and is often used after ACLR to assess quadriceps hypertrophy.⁴⁴ All subjects will be supine with the knee in full extension. The average of 3 measurements will be recorded with the starting point 10cm superior to the superior pole of the patella.

10 Repetition Max Test: The 10 repetition max test will be used to determine an estimate 1 rep maximum on the Shuttle Leg Press machine, as this is a safe and reliable alternative to predicting a 1 rep maximum. This will allow for exercise prescription.⁴⁵ All participants will complete a double leg and single leg Shuttle leg press 10 repetition maximum. The test will follow the protocol as recommended by the National Strength and Conditioning Association.⁴⁶

Isometric thigh strength: Preoperative, 8 week, 12 week, 6 month, and return to play assessments will measure maximum isometric muscle torque using an isokinetic dynamometer (Humac CSMi USA, Stoughton, MA, USA). Patients will complete 3 trials with each knee in 60° of flexion and will be allowed a 5-second rest period between trials. The uninvolved limb's quadriceps and hamstring strength will be tested first, followed by the involved limb. Patients will be given verbal encouragement throughout the test to provide maximal effort. The highest peak torque measurement of the five trials will be collected and recorded in newton-meters (Nm). These peak torque values will be used to calculate the Limb Symmetry Index (LSI), or the ratio between the involved limb and uninvolved limb and expressed as a percentage. Peak torque will subsequently be normalized to the patient's body mass (kilogram) and recorded for analysis (Nm/kg).

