- c. For the long arc quadriceps (LAQ) progression, all exercises will start with no external resistance and after every 2 sessions weight will be increased by 1 pound. For the Shuttle progression, exercises will start at 30% of patients 1RM. An estimated single leg and double leg 1 repetition max will be determined at pre-operative visit. Patients unable to complete the prescribed dosage will complete the exercise using both limbs on the Shuttle and will use a ratings of perceived exertion (RPE) scale to determine intensity. RPE has been shown to be an effective tool to individualize exercise prescription and load progression.⁵⁶
- d. The standing straight leg raise exercise will be completed from week 0-2 unless the patient is able to demonstrate 10 straight leg raise repetitions with minimal extensor lag. All standing exercises will be standardized to complete in the same position to have minimal compensation.
- e. Discontinuation or stoppage of exercise: Patients will be instructed to attempt to complete all exercises. Should the patient be unable to tolerate 80% limb occlusion or report lower extremity paresthesia, the therapist will reduce occlusion by 5mmHg between exercise sets. Should the patient reach less than 60% limb occlusion, the exercise will be stopped.
- f. At the completion of both exercises, patients will be asked to rate RPE, pain on a visual analog scale, and report from a list of documented adverse events.

Control Group: All exercises will be completed in the manner described above without the use of the Delfi BFR device. Exercise volume, progression, and discontinuation will be determined in the same manner.

Sample Size/Power Analysis: Based on our preliminary work evaluating differences between isometric quadriceps strength at 3 and 6 months after ACLR in adolescents, an a priori power analysis for a two-way Version 1.2_.1.8.2023

repeated measures analysis of variance (within-between interaction) was conducted using an alpha level of 0.05, power of 0.80 and moderate effect size (0.6). The projected sample size needed to determine differences between groups was determined to be 14 total individuals. Thus, we have increased the sample size to 40 (20 per group) to allow for even group numbers and to account for possible attrition.

Data analysis

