Data will be collected on all patients enrolled into the study. Descriptive statistics will be generated on the demographic characteristics of both treatment groups. We will use a two-way repeated measures analysis of variance to determine the effect of treatment groups, BFRT compared to standard of care therapy, over time on subjective and objective outcomes. Exact analysis for each test will depend on variance and distribution/normality of data set. This will be achieved using the Statistical Package for the Social Sciences (SPSS) software version 27.0 (IBM Corp., Armonk, NY, USA). We will address each aim in the following manner.

Accrual and Expected Duration of Accrual

Once approved, we expect that this study can be accomplished within two to three years. The open period for this study will be between February 2022 and February 2025.

Study Limitations:

There are several limitations anticipated with this study that will impact its power and external validity. These limitations include an inherent sampling bias with our recruitment strategy, lack of patient or participant blinding, and small sample size.

Attempts will be made to reduce any potential bias by having standardized educational scripts regarding BFR training that each treating therapist will read to subjects prior to their first BFR session.

Subjects in our study will likely come from the same surgeons and the same type of ACL graft (QT). This could be a potential limitation in the generalizability of our results to other surgeons and graft types.

Administrative Organization

Roles and responsibilities:

[name], PT, DPT: Will serve as the study's primary investigator. [name] will provide primary support for the SRC and IRB study protocol development and submission, as well as maintaining updates and compliance with clinicaltrials.gov. He will review the required databases and pull the relevant data required to complete this study. He will also aid in data interpretation and manuscript preparation.

All MDs listed: The MDs listed on this proposal will be responsible for recruitment of patients, data interpretation and manuscript preparation.

All physical therapists listed: The PT's listed on this proposal will serve as the study's co-investigator. They will provide support in development of SRC and IRB documents (review of literature). They will help with data collection, recruitment, consenting patients.

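### The repeated-measures ANOVA makes no use of the pre-operative isometric value as a covariate and names no term for hypotheses 1a and 1b; a baseline-adjusted post-operative contrast would gain power from data already collected

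*Protocol*

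**What the plan says.** The Protocol's Data analysis section uses a "two-way repeated measures analysis of variance to determine the effect of treatment groups, BFRT compared to standard of care therapy, over time" for subjective and objective outcomes alike. It adds that the exact analysis will depend on how the data are distributed. It then announces "We will address each aim in the following manner", but the next heading follows at once and no text by aim is given.

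The only ANOVA term named anywhere is in Sample Size/Power Analysis, where the calculation for a two-way "repeated measures analysis of variance (within-between interaction) was conducted using an alpha level of 0.05". Its basis is preliminary work "evaluating differences between isometric quadriceps strength at 3 and 6 months after ACLR in adolescents".

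The hypotheses concern named post-operative visits. Under 1a, isometric torque and limb symmetry "will be greater in the BFRT group compared to the control group at 8 and 12 weeks after ACLR". Under 1b, "isokinetic knee extension peak torque and limb symmetry will be greater in the BFRT group compared to the control group at 6 months" and at return to sport. Hypothesis 1c concerns the change in strength from before surgery to 8 weeks.

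On measurement, the Isometric thigh strength paragraph states: "Preoperative, 8 week, 12 week, 6 month, and return to play assessments will measure maximum isometric muscle torque". The Data Collection section lists "five different time points during the rehabilitation process: preoperatively, 8 weeks, 12 weeks, 6 months, and time of return to play". Table 1 places isokinetic testing at 6 months and return to play only.

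**The concern.** In a randomised trial the expected group difference before surgery is zero. If that visit is one of five levels of the time factor, it pulls the group main effect towards zero and contributes to an interaction test with four degrees of freedom. As a covariate, the same measurement removes between-patient variance from the comparison that 1a asks about. The Protocol does not say outright that the pre-operative visit is a time level, but it is the natural reading of its five time points.

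The open choice of term also matters for 1b. Isokinetic strength has two visits, and a benefit of equal size at both leaves nothing for a group-by-time interaction to detect. With 40 patients, and a small sample listed by the Protocol among its own limitations, the choice of contrast decides how much a null result would mean.

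**Working it through.** **The plan's own figure.** The Protocol gives alpha 0.05, power 0.80, effect size 0.6 and 14 patients in total, raised to 40 (20 per group). It does not give the number of visits, the correlation or the effect-size metric. For the within-between interaction with k visits, λ = f²·N·k/(1−ρ).
- f = 0.6, k = 2, ρ = 0, N = 14: λ = 0.36 × 14 × 2 = 10.08 on F(1,12), power 0.83. N = 12 gives 0.75. So 14 is reproduced.
- f = 0.3 (that is, d = 0.6), k = 3, ρ = 0.7, N = 14: λ = 0.09 × 14 × 3 / 0.3 = 12.6 on F(2,24), power 0.86. N = 12 gives 0.78. So 14 is reproduced again.

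The stated 14 therefore does not settle what 0.6 means.

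**Assumptions for the comparison (not in the Protocol).** n = 20 per group; no difference before surgery and d = 0.6 SD at every post-operative visit; equal correlation ρ among all visits, baseline included; two-sided alpha 0.05.

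**Formulas**, with d_t the difference at visit t and d̄ its mean:
- Interaction: λ = (n/2)·Σ(d_t − d̄)²/(1−ρ), F(k−1, 38(k−1)).
- Group main effect: λ = (n/2)·d̄²/[(1+(k−1)ρ)/k], F(1,38).
- Adjusted mean of two visits: λ = (n/2)·d²/[(1+ρ)/2 − r²], F(1,37), with r the correlation with baseline.
- Adjusted single visit: the same with variance 1 − r².

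**Hypothesis 1a at ρ = r = 0.5.**
- Five-visit interaction: d̄ = 0.48 and Σ(d_t − d̄)² = 0.48² + 4 × 0.12² = 0.288, so λ = 10 × 0.288/0.5 = 5.76; power 44%.
- Five-visit main effect: λ = 10 × 0.48²/0.6 = 3.84; power 48%.
- Unadjusted mean of 8 and 12 weeks: λ = 10 × 0.36/0.75 = 4.80; power 57%.
- Adjusted mean: λ = 10 × 0.36/(0.75 − 0.25) = 7.20; power 74%.

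| Test, d = 0.6 | ρ = 0.3 | ρ = 0.5 | ρ = 0.7 |
|---|---|---|---|
| 1a, five-visit interaction | 32% | 44% | 68% |
| 1a, five-visit main effect | 61% | 48% | 40% |
| 1a, unadjusted 8/12-week mean | 63% | 57% | 52% |
| 1a, adjusted 8/12-week mean | 69% | 74% | 87% |
| 1c, change from before surgery to 8 weeks | 35% | 46% | 67% |
| 1c, adjusted 8-week difference | 49% | 57% | 73% |
| 1b, interaction, constant benefit | 5% | 5% | 5% |
| 1b, main effect, constant benefit | 63% | 57% | 52% |

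Simulation with 20,000 trials per cell gave 68 / 73 / 86% for the adjusted 8/12-week mean, so the closed form is about one point optimistic. The 5% for 1b is algebra: d_t − d̄ = 0 at both visits, so λ = 0 whatever the effect size.

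**Where the gain shrinks or reverses.**
- Visit ρ 0.5 but baseline correlation 0.2 or 0.3: the variance is 0.75 − 0.04 = 0.71 or 0.75 − 0.09 = 0.66, and power is 59% or 62% against 57% unadjusted, a gain of 2 to 5 points.
- Isometric benefit at 8 and 12 weeks only: the five-visit interaction has 47 / 63 / 87% and the five-visit main effect 20 / 16 / 14%. The adjusted mean stays at 69 / 74 / 87%, so at ρ = 0.7 it gains nothing over the interaction.
- All correlations zero, sustained benefit: the five-visit main effect (91%) beats the adjusted mean (73%), and adjustment costs about one point against the unadjusted mean (74%).
- Isokinetic benefit of 0.6 SD at 6 months that fades to zero by return to play: the interaction has 35 / 46 / 67% and the main effect 21 / 19 / 17%.

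**The case against.** The strongest objection is that terms, contrasts and covariates are commonly settled in a statistical analysis plan, which may exist here. That stands as far as naming the term goes: silence alone would be no finding. What remains is that the Protocol itself chooses a model for all outcomes, and a better use of a measurement it already schedules is available. Its allowance for changing the analysis concerns distribution, not baseline adjustment.

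Four stronger readings are tempting and are not supported.
- A reader might infer that 1b will be tested by the interaction. No passage says so; that term appears only in the sample-size routine, for isometric strength. The 5% is what would happen if it were used.
- A reader might infer that the pre-operative value can serve every strength outcome. Isokinetic strength has none; pre-operative isometric torque is at most a proxy of unknown value.
- A reader might infer that the gain holds whatever 0.6 means. It does not. In a two-group, two-visit interaction, f = 0.6 is a difference in change of 4f = 2.4 SD. At that size even the five-visit main effect against a benefit at 8 and 12 weeks only has 99 / 97 / 92% power, and little is left to gain.
- A reader might infer that the ANOVA is biased or invalid. It is neither.

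Two further points stand in part. Hypothesis 1c is worded as a change, so the change test is its literal match; the adjusted 8-week difference is more efficient but overlaps 1a. Averaging 8 and 12 weeks condenses a hypothesis that names both visits, so each visit should also be reported.

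**Conclusion.** The concern holds as an improvement in efficiency and alignment, worth making but not a flaw that invalidates the analysis. With 20 per group, a sustained 0.6 SD benefit and baseline correlation equal to the visit correlation, adjustment raises power for 1a over the unadjusted 8/12-week mean by about 6, 17 and 35 points at correlations of 0.3, 0.5 and 0.7. The adjusted contrast also exceeds both five-visit ANOVA terms there. With a baseline correlation of only 0.2 to 0.3 at visit correlation 0.5, the gain falls to 2 to 5 points.

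For 1b the point is narrower: the group main effect matches the hypothesis and can detect a constant benefit, while the interaction cannot. A benefit that fades by return to play would favour the interaction. The correlations, the effect pattern and the reading of 0.6 as a standardised difference are assumptions; the Protocol fixes none of them.

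**What to change.** Complete the unfinished sentence in the Data analysis section along these lines.
- **Isometric outcomes:** analyse the post-operative visits with group, visit and group-by-visit, and the pre-operative value of the same outcome as covariate, by linear mixed model or ANCOVA in SPSS, which the Protocol already names.
- **1a:** test the adjusted group difference averaged over 8 and 12 weeks, and report each visit with an interval.
- **1c:** report the baseline-adjusted 8-week difference and note that it overlaps 1a.
- **1b:** test the group difference averaged over 6 months and return to play (the group main effect), and report each visit. Pre-operative isometric torque may be added as an optional proxy covariate.
- If the ANOVA is kept, fit it to the hypothesised post-operative visits only and name the group main effect as the test of 1a and 1b.

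Naming contrasts does not remove multiplicity across torque, limb symmetry and the two isokinetic speeds, so also state which comes first or how alpha is adjusted. The cost is analysis wording: no extra patients, visits or software.
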